### **IGA mod 2011 score over time**

Summary statistics for the IGA mod 2011 score over time will be presented by visit and treatment group in contingency tables.

The IRT dosing error affected subjects will be listed for IGA mod 2011 score.

### **CDLQI 0 or 1 achievement**

Summary statistics will be provided for number of subjects achieving CDLQI 0 or 1. Secukinumab groups will be compared to controls (placebo or active) by means of Fisher's exact test. Figures will also be provided. Additional analysis will be performed for CDLQI results by IRT dosing error. See [Section 4.1](#) for details.

#### **2.7.4 Handling of missing values/censoring/discontinuations**

Not applicable.

### **2.8 Analysis of secondary efficacy objective(s)**

#### **2.8.1 Secondary endpoints**

Same instructions as for primary endpoints.

#### **2.8.2 Statistical hypothesis, model, and method of analysis**

Not applicable.

#### **2.8.3 Handling of missing values/censoring/discontinuations**

Not applicable.

### **2.9 Safety analyses**

All safety analyses will be based on the safety set. Only those visits which were pre-planned in the protocol will be reported in tables and figures for safety variables.

In general, the following guidelines will be considered for safety analysis:

- Adverse events: Only treatment emergent records are reported in tables, and all AE events will be listed with “treatment emergent” flag displayed.
- Laboratory data (including vital sign and ECG):
  - by period summary statistics tables: only include “on-treatment” records in the tables, i.e., assessments within last dose plus 84 days cutoff. Listings will have the “on-treatment” flag displayed.

In addition to the treatment emergent and on-treatment safety summary, extended entire study period safety analysis may be provided for AE records up to end of study (EOS) and for laboratory by visit summary statistics up to EOS.

### **Treatment groups for evaluation**

The summaries of evaluation will be reported for both induction period and entire treatment period or up to week 24 maintenance period will also be reported, for Week 24 PEA. Treatment period up to week 52 including both induction period and maintenance period will be reported for week 52 analysis. A number of selected safety analyses will be reported for entire study period, which covers the study period from randomization to end of study. The treatment following groups will be used:

- for induction period:
  - AIN457 Low dose, AIN457 High dose, Placebo, Etanercept;
- for maintenance treatment period (or up to week 24/52):
  - by-visit summary: AIN457 Low dose, AIN457 High dose, Placebo to AIN457 Low dose, Placebo to AIN457 High dose, Etanercept, Any AIN457 dose.
  - by-period summary: AIN457 Low dose, AIN457 High dose, Any AIN457 low dose, Any AIN457 high dose, Etanercept, Any AIN457 dose.
- for entire treatment/study period:
  - Any AIN457 low dose, Any AIN457 high dose, Any AIN457 dose, Etanercept\*.

\*Of note, for subsequent analyses beyond week 52 analysis, Etanercept will only be presented in EAIR

Safety analyses will be performed on treatment received or actual treatment (See [Section 2.2: Safety set](#)).

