### **Extension Treatment Epoch**

The extension treatment epoch is defined as Week 52 (from dosing) until Week 236. At this epoch the subjects are all treated with secukinumab and the purpose is the collection of long term safety and efficacy data.

At the end of the maintenance epoch, all subjects on secukinumab will enter the extension treatment epoch of the study and will continue to receive the same dose of secukinumab they had received at completion of maintenance epoch.

Subjects who participated in the maintenance epoch but prematurely discontinued the study will not be able to enter the extension treatment epoch of the study. Patients receiving etanercept will not be eligible to enter the extension treatment epoch. Instead, at Week 52, they will complete an EOM visit and then enter the post-treatment follow-up epoch. The first secukinumab dose of the Extension Treatment epoch is administered at Week 52. Subsequent doses of secukinumab will be administered every four weeks until the End of Treatment (EOT). For subjects who discontinue study treatment for any reason before the end of the extension treatment epoch, the End of Extension Treatment (EOT) visit should be performed approximately 4 weeks after their last dose of secukinumab. The subject will then enter the post-treatment follow-up epoch (perform F4, F8, F12 and F16 visits). If subjects start another systemic anti psoriatic treatment during follow up, they do not need to continue with the remaining follow-up visits but they will be expected to return to site after the start of the systemic treatment and perform End of Follow-up (EOF) visit.

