 If the first QuantiFERON® TB-Gold In-Tube test is indeterminate, the investigator may choose to perform a second QuantiFERON® TB-Gold In-Tube test (as part of an unscheduled visit) or refer the subject for tuberculosis workup per local guidelines. If the result of any QuantiFERON® TB-Gold In-Tube test is "positive" or the results of 2 sequential QuantiFERON® TB-Gold In-Tube tests are "indeterminate", the subject must be referred to have a tuberculosis workup per local guidelines (if no workup within 12 weeks prior to randomization is available). The subject will not be eligible for randomization if "active tuberculosis is present "or if "latent tuberculosis is present and is untreated as per local guidelines." No QuantiFERON® TB-Gold In-Tube test is to be done at the central laboratory after the subject has been randomized.

 Serum pregnancy tests will be performed at screening and urine pregnancy test at all other scheduled visits. If there is a positive urine pregnancy test, study treatment must be withheld and a serum pregnancy test done at the same visit. Pregnancy tests will be performed in female subjects of child bearing potential, i.e. those who have started menstruation and/or are of age 12 or older.

 Optional assessment. Chest X-ray or chest MRI (at prespecified sites) may be performed based on the investigator's judgment, to assess presence of infections or malignancies.

[REDACTED]

 Text only version will be used in all subjects. Assessment will no longer be performed once subjects reach 18 years of age.

 At visit 2 the PASI Score and BSA must be calculated by efficacy assessor/appropriate site staff prior to contacting IRT. The investigator must ensure subject meets all eligibility criteria before contacting IRT to randomize the subject. At Visit 8 (week12), the site should have the PASI 75 responder status calculated prior to contacting IRT to communicate it.

 For every visit (including unscheduled), weight measured at that visit will be entered into IRT.

 Etanercept will be administered weekly up to and including Week 51. Outside of site visits, administration should preferable occur at home by subject, or caregiver. Alternatively if subject/parent does not feel confident in performing study treatment administration at home, they are allowed to receive study treatment administration at site.

[REDACTED]

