### 1.1 Study design

This is a multicenter, randomized, double-blind, placebo-and active-controlled (etanercept in single blinded arm) study in pediatric subjects aged 6 years to less than 18 years with severe chronic plaque psoriasis. Approximately 160 subjects aged 6 years to <18 years will be enrolled, of which at least 30 pediatric subjects will be 6 years to <12 years old. In reality around 40-45 patients will be needed to meet the requirement of recruiting about 30% of subjects in the < 25kg weight group.

Subjects will be randomized using a 1:1:1:1 ratio into one of the treatment arms: secukinumab low dose, secukinumab high dose, etanercept or placebo. The randomization will be stratified by age (<12 years or ≥12 years) and weight (<25 kg, 25-<50 kg, ≥50kg) at randomization. Subjects randomized to the placebo group will be pre-assigned to either the low- or high-dose group of secukinumab, at the Randomization visit, in case they are not achieving a PASI 75 response as assessed at Week 12.

The study consists of 5 Epochs: screening (up to 4 weeks), induction (of 12 weeks), maintenance (of 40 weeks), extension treatment epoch (open-label of 184 weeks) and post-treatment follow-up epoch (of 16 weeks). The detailed information of the study design is described in [Figure 1-1](#).

**Figure 1-1** Study design

The following study periods will be considered for analysis:

- **Screening period** (before Randomization)
- **Induction period** (Randomization to Week 12 pre-dose), including follow-up period (F4, F8, F12 and F16 (EOF) visits) for prematurely discontinued subjects before Week 12 completion. For placebo PASI 75 responders at Week 12, subjects will enter follow-up period after Week 12, including the first visit F4 and four weeks later visit EOF at F8.
- **Maintenance period** (Week 12 dose to Week 52 pre-dose), including follow-up period (F4, F8, F12 and F16 visits) for prematurely discontinued subjects before Week 52 completion, and for etanercept patients with the completion of the maintenance epoch.
- **Extension period** (Week 52 dose until Week 236 (EOT)), including follow-up period (F4, F8, F12 and F16 visits) for prematurely discontinued subjects before Week 236 completion.
- **Entire treatment period** (Randomization to Week 236 (EOT)), for safety analysis, exposure including follow-up period up to last dose + 84 days.
- **Entire study period** (Randomization to end of study (EOS)), including follow-up period (F4, F8, F12 and F16 visits).

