**Table 2-11      Overview of analyses on some safety endpoints**

| Analysis Period                    | AEs & important risks                                | SAEs & important risks                               | AES-SMQ  | AEs by severity   | study treatment related AEs, death & other significant AEs | Notable (lab/vitals/ECG) |
|------------------------------------|--|--|--|-------------------|--|--------------------------|
| Induction Period (Day 1 -Week 12)  | • crude incidence                                    | • crude Incidence                                    | • crude incidence                                    | • crude incidence | • crude Incidence  | • crude incidence        |
| Maintenance Period (up to week 52) | • crude incidence                                    | • crude Incidence                                    | • crude incidence                                    | • crude incidence | • crude Incidence  |                          |
| Entire treatment                   | • crude incidence
• exp. time adjusted Incidence* | • crude incidence
• exp. time adjusted Incidence* | • crude Incidence
• exp. time adjusted Incidence* | • crude incidence | • crude Incidence
• exp. time adjusted Incidence*       | • crude Incidence        |
| Entire study                       | • exp. time adjusted Incidence*                      | • exp. time adjusted Incidence*                      |  |                   |  |                          |

\*Note: exposure adjusted incidence rates will be provided and follow the guideline as below:

- Primary SOC level for AE and SAE
- Level 1 for risks and SMQ
- PT level for SAE
- PT level for AE  $\geq 4\%$ , or events that had an incidence rate of at least 5.0 cases per 100 subject-years in one of any treatment group
- Other selected AEs on lower levels (e.g. PT or SMQ level 2), if **appropriate**

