**Exposure adjusted incidence rates will be also provided for the entire treatment period, by the following subgroups:**

- Treatment emergent AEs by SOC, PT and by age strata
- Treatment emergent AEs by SOC, PT and by body weight strata
- Treatment emergent SAEs by SOC, PT and by age strata
- Treatment emergent SAEs by SOC, PT and by body weight strata
- Important identified and potential risks (level 1) based on all adverse events by age strata
- Important identified and potential risks (level 1) based on all adverse events by body weight strata

The crude incidence of treatment emergent adverse events will be summarized by primary system organ class and preferred term. Confidence intervals for the crude rate will be derived as described in [Section 5.1](#). In addition, exposure time-adjusted rates (incidence rate) including 95% confidence intervals may be provided.

AEs and serious AEs will be summarized by presenting, for each treatment group (including any AIN457), the number and percentage of subjects having any AE, having an AE in each primary system organ class and having each individual AE (preferred term). Summaries (crude incidences only) will also be presented for AEs by severity. If a particular AE 'severity' is missing, then this variable will be listed as missing and treated as missing in summaries. If a subject reported more than one adverse event with the same preferred term, then the adverse event with the greatest severity will be presented. If a subject reported more than one adverse event within the same primary system organ class, then the subject will be counted only once with the greatest severity at the system organ class level, where applicable.

AEs and SAEs will be presented in terms of exposure time-adjusted incidence rates with 95% confidence intervals for entire study period (up to EOS).

Adverse events will also be summarized by standardized or customized MedDRA queries (SMQ or CMQ/NMQ). The MedDRA version used for reporting the adverse events will be described in a footnote.

The most common adverse events reported ( $\geq z\%$  in any group for each preferred term in the table by SOC and PT or  $\geq z\%$  in any group for each grouping term table) will be presented in descending frequency according to its incidence in secukinumab group starting from the most common event. Here, the threshold value  $z$  is set to 4 (%) but it may be updated following review of the dry run outputs.

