## **2.15.5 Interim analysis**

[figure not shown]
Apart from the final analysis, the study is also planned with two full analyses.

The first full analysis will be performed when all patients completed the Week 24 visit. And the next full analysis will be performed when all patients completed the Week 52 visit (i.e. Maintenance period).

The data cut-off date for the Week 24 PEA is the date of the last Week 24 visit for study subjects, i.e. 7 March 2019. The Week 24 PEA will include all efficacy data up to week 24

visit for each individual subject. For inclusion of safety data, we apply individual data cut-off of each subject to maximize use of available data. Thus for each subject, we will include all safety data collected until the last visit of the subject prior to the PEA data cut-off of 7 March 2019.

The data cut-off date for the Week 52 interim analysis is the date of the last Week 52 visit for study subjects, i.e. 18 September 2019. The Week 52 interim analysis will include all efficacy data up to week 52 visit for each individual subject. For inclusion of safety data, we apply individual data cut-off of each subject to maximize use of available data. Thus for each subject, we will include all safety data collected until the last visit of the subject prior to the interim analysis data cut-off of 18 September 2019.

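### At the Week 52 analysis, crude entire-treatment-period tables set etanercept (about 63 weeks at most) beside secukinumab followed to the calendar cut-off, and notable lab and ECG values have no listed equal-window table after Week 12

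*SAP*

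**What the plan says.** - **Groups shown.** For the entire treatment or study period, SAP 2.9 (Treatment groups for evaluation) lists the columns "Any AIN457 low dose, Any AIN457 high dose, Any AIN457 dose, Etanercept", and Table 2-1 agrees. A note there and footnote c of Table 2-1 limit etanercept to exposure-adjusted rates, but only later: "for subsequent analyses beyond week 52 analysis, Etanercept will only be presented in EAIR".
- **Cut-off.** SAP 2.15.5 does not truncate safety data at the analysis week. For the Week 52 analysis, "we will include all safety data collected until the last visit of the subject prior to the interim analysis data cut-off" of 18 September 2019; the same rule applies to the Week 24 analysis at 7 March 2019.
- **Etanercept exposure.** Protocol Table 6-1, footnote 15: "Etanercept will be administered weekly up to and including Week 51". Protocol 3.1: "Patients receiving etanercept will not be eligible to enter the extension treatment epoch". SAP 1.1 defines the entire treatment period "for safety analysis, exposure including follow-up period up to last dose + 84 days".
- **Metrics.** In Table 2-11 ("Overview of analyses on some safety endpoints"), the entire-treatment row gives crude and exposure-adjusted incidence for AEs, SAEs, SMQs, and related AEs, deaths and other significant AEs. AEs by severity and notable lab, vital-sign and ECG values get crude incidence only. SAP 2.9.1 confirms this for severity: "Summaries (crude incidences only) will also be presented for AEs by severity".
- **Up-to-Week-52 row.** Table 2-11 fills this row for AEs by severity and leaves it blank for notable values. SAP 2.9.4.2 separately plans notable vital signs up to Week 52. The laboratory (2.9.3) and ECG (2.9.4.1) sections name no such table for notable values.

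**The concern.** The chance that a child has ever had a notable value, or a worse severity grade, grows with time observed. Two crude percentages over different lengths of follow-up therefore differ even when the underlying risks are the same. Here the entire-period columns stop early for etanercept and run on for secukinumab. In expectation etanercept looks safer, and a true difference in the other direction could be masked.

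The SAP already uses the remedy, exposure-adjusted rates only for etanercept, but starts it one analysis late. The gap matters most for notable lab and ECG values. Table 2-11 lists neither an exposure-adjusted rate nor an up-to-Week-52 table for them, so beyond Week 12 a reader has only the unequal-window percentages.

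**Working it through.** The documents give no figure for observation time by arm, so there is none to reproduce.

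**Etanercept maximum.** The last dose at Week 51 falls on Day 1 + 51×7 = Day 358. Adding 84 days gives Day 442, that is (357 + 84)/7 = 63 weeks after Day 1, or about 1.21 years.

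**Longest secukinumab follow-up.** No one was enrolled at Amendment 1 (April 2015) and 4 were randomised by Amendment 2 (February 2016). First randomisation therefore lies between about end April 2015 and end February 2016. The longest-followed secukinumab child has 3.55 to 4.4 years at 18 September 2019, and 3.0 to 3.9 years at 7 March 2019.

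**Accrual (assumed between anchors).** The anchors are 4 by February 2016, 120 by April 2018 (Amendment 3), and 160 by 19 September 2018 (last Week 52 visit minus 364 days). Three curves pass through them:
- even: straight lines between anchors;
- back-loaded: only 20 by December 2017;
- front-loaded: 100 by February 2017.

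**Formula.** With equal constant hazard h, expected crude incidence is the mean over children of 1 − exp(−h·t). For etanercept, t is the smaller of time to cut-off and 63 weeks. For originally randomised secukinumab it is time to cut-off, and for placebo switchers 12 weeks less. Any secukinumab is (80 × original + 40 × switchers)/120. Event hazards are not in the documents; h = 0.10 per year is an assumption, varied below.

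Check by hand: a mean of 62.3 weeks is 1.194 years, and 1 − exp(−0.1194) = 11.3%.

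No dropout, h = 0.10 per year:

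| Analysis | Accrual | Mean weeks, etanercept | Mean weeks, original secukinumab | Ratio | Crude, etanercept | Crude, Any secukinumab |
|---|---|---|---|---|---|---|
| Week 52 | even | 62.3 | 115.6 | 1.85 | 11.3% | 19.0% |
| Week 52 | back-loaded | 62.3 | 87.3 | 1.40 | 11.3% | 14.6% |
| Week 52 | front-loaded | 62.3 | 130.5 | 2.09 | 11.3% | 21.2% |
| Week 24 | even | 55.2 | 87.7 | 1.59 | 10.0% | 14.5% |
| Week 24 | back-loaded | 51.7 | 59.5 | 1.15 | 9.4% | 9.9% |
| Week 24 | front-loaded | 55.8 | 102.6 | 1.84 | 10.1% | 16.9% |

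**Sensitivity at Week 52:**
- h = 0.05: 5.8% against 7.6-11.3%.
- h = 0.30: 30.1% against 37.3-49.9%.
- h = 0.10 with 10% discontinuation per year: 10.8% against 13.7-19.0%.

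**Equal window.** If follow-up is cut at Week 52 in each randomised arm, h = 0.10 gives 1 − exp(−0.10 × 364/365.25) = 9.5% in each.

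**Sampling.** Notable labs are found only when blood is drawn. Protocol Table 6-1 has 15 post-baseline hematology draws to Week 52 (Weeks 2, 4, 8, 12, 14, 16, then every 4 weeks). Table 6-2 adds only Weeks 64, 76, 88 and 104 for a child followed to Week 115. That is 19 against 15 before etanercept follow-up draws, a ratio of about 1.3 where the even-accrual time ratio is 1.85. Chemistry is drawn less often during maintenance, so its ratio is larger.

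**The case against.** The strongest reply is that most of the safety plan already handles this. AEs by severity have an up-to-Week-52 crude table with an etanercept column, and notable vital signs have one under SAP 2.9.4.2. AEs, SAEs, SMQs and deaths have exposure-adjusted rates for the entire period. Table 2-11 is an overview, so a blank cell need not mean that nothing is planned; SAP 2.9 promises up-to-Week-52 reporting for safety summaries without excepting labs, and by-visit lab summaries compare arms at matched visits. The safety objective is against placebo, and Protocol 3.4 plans no formal comparison with etanercept.

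Much of this stands. A reader might infer that severe AEs and vital signs also lack an equal-window comparison. They do not: for them the problem is confined to the entire-period table. A reader might also infer that the Week 24 submission analysis is certainly affected. The sentence in SAP 2.9 on Week 24 can be read as entire period or up to Week 24, so this depends on which tables are produced. The longest follow-up, about 3.5 years or more, describes the first children randomised; the mean gap is much smaller.

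What does not stand is that the notables gap is only cosmetic. The general statement in SAP 2.9 names no lab or ECG notables table, and by-visit means do not replace incidence of notable values. Without a formal comparison, side-by-side percentages are what readers will use.

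**Conclusion.** The concern holds for the Week 52 analysis, with notable lab and ECG values as the core: no listed equal-window crude comparison with etanercept after Week 12, and no exposure-adjusted rate. For AEs by severity and notable vital signs it holds only for the entire-period table. For Week 24 it is conditional on entire-period tables being produced.

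At an assumed equal hazard of 10 per 100 patient-years, expected crude incidence at Week 52 is about 11% for etanercept against about 15-21% for Any secukinumab. At Week 24 it is about 9-10% against 10-17%, with almost no gap if accrual was back-loaded. These figures rest on inferred accrual, constant and equal hazards, 160 children, no dropout and all 40 placebo children switching. With 10% annual discontinuation the direction is unchanged. For lab notables, sparser extension sampling may make the gap smaller than the time ratio suggests.

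A reader might infer that etanercept will necessarily show fewer events. The documents do not support that: the bias is in expectation, and with about 40 etanercept children chance could reverse it in any one table. No decision rule uses these tables, but the plan as written builds in a bias that is cheap to remove, so the change should be made.

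**What to change.** 1. Apply the existing rule that etanercept appears only as exposure-adjusted rates to the entire-treatment-period tables at the Week 24 and Week 52 analyses as well.
2. In Table 2-11, add crude incidence of notable lab and ECG values from Day 1 to Week 52 pre-dose in every arm. State the pre-dose cut explicitly, because SAP 1.1 includes follow-up visits in the maintenance period for etanercept completers. Compare etanercept with the originally randomised low- and high-dose columns, which SAP 2.9 already lists for this period.
3. If etanercept stays in the entire-period tables for severity and notable values, add exposure-adjusted rates there, using the method in SAP 5.1.4.

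Cost: SAP wording and a few extra tables from data already collected. The crude entire-period tables lose their etanercept column. The current SAP (December 2020) postdates both cut-offs, so the practical form is supplementary tables plus a caveat in the report that the crude entire-period percentages cover unequal follow-up.
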